Scores: We will use CDW data to calculate a cardiovascular risk score designed by the Framingham Heart Study,^{66,67} which incorporates age, BMI, systolic blood pressure, antihypertensive medication use, current smoking, and diagnosis of diabetes. The non-laboratory risk score replaces lipid values with BMI and is comparable to the standard Framingham Risk score in predicting cardiovascular events.⁶⁷ The non-laboratory Framingham score is particularly well-suited to pragmatic trials using data collected in usual care, and is responsive to weight loss interventions.⁶⁸ Our group has extensive experience in obtaining each of the required data elements from CDW.⁵¹ We will also supplement collection of information about current antihypertensive use, smoking, and diabetes status with participant self-report on baseline and 3, 12, and 21 month follow-up surveys. Blood pressure: We will obtain diastolic and systolic values from the CDW. Based on prior work in an ongoing trial, we anticipate >80% of subjects will have clinical follow-up measures (Section 2.5). PAP Adherence: We will explore the impact of weight loss on PAP usage and will assess PAP use as a mediator in secondary analyses of the intervention's impact on primary and secondary outcomes.¹⁴ All PAP machines dispensed by VA transmit adherence, with results accessible in routine care through secure platforms.^{69,70} We will collect 90-day PAP adherence at 3, 12 and 21 months. We also collect self-reported adherence to PAP and other treatments at 3, 12, and 21 months.

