$$Y_{ii} = \beta_0 + \beta_1 T_i + \beta_2 X_i T_i + \beta_3 Q_i + \beta_4 A_i + u_i + \epsilon_{ii}$$

which models for each patient i their measure for each outcome (FOSQ and weight separately), incorporating time of measurement T_j (0 or 12 months), treatment by time interaction $X_i T_j$, stratification variables Q_i , and adjustment variables A_i including age, gender, race, Charlson comorbidity index, and rurality. The model will include a random normal intercept u_i for each patient and a random normal error term ϵ_{ij} , all assumed independent. The variances of the ϵ_{ij} will be assumed different at baseline and 12 months. Here, β_0 is the average baseline FOSQ/weight among the control and treatment groups combined (assumed equal due to randomization), β_1 is the expected change in FOSQ/weight over time in the control group, and β_2 , the quantity of interest in hypothesis H1, is the expected difference in the change in FOSQ/weight over time between the treatment and control groups, or equivalently the expected difference between groups at 12 months. In secondary analyses, we will incorporate primary and secondary outcomes from each time point (baseline, 3, 12, and 21 months). We will use the same model to test secondary outcomes captured only at follow up, omitting baseline values.

Additional Analytic Subgroups:

- 1) Subgroups defined by each of the pre-specified strata.
- 2) Subgroups defined by gender.
- 3) Patients who are prescribed continuous positive airway pressure and use <4 hours per night in the 90 days before the outcome period
- 4) The subgroup of patients who are prescribed continuous positive airway pressure and use ≥4 hours per night in the 90 days before the outcome period.

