which models for each patient i their measure for each outcome (FOSQ and weight separately), incorporating time of measurement T_j (0 or 12 months), treatment by time interaction $X_i T_j$, stratification variables Q_i , and adjustment variables A_i including age, gender, race, Charlson comorbidity index, and rurality. The model will include a random normal intercept u_i for each patient and a random normal error term ϵ_{ij} , all assumed independent. The variances of the ϵ_{ij} will be assumed different at baseline and 12 months. Here, β_0 is the average baseline FOSQ/weight among the control and treatment groups combined (assumed equal due to randomization), β_1 is the expected change in FOSQ/weight over time in the control group, and β_2 , the quantity of interest in hypothesis H1, is the expected difference in the change in FOSQ/weight over time between the treatment and control groups, or equivalently the expected difference between groups at 12 months. In secondary analyses, we will incorporate primary and secondary outcomes from each time point (baseline, 3, 12, and 21 months). We will use the same model to test secondary outcomes captured only at follow up, omitting baseline values.

Additional Analytic Subgroups: In addition to analyses of the entire sample using intent to treat, we will analyze primary and secondary outcomes according to model 1 and model 2 in the following groups:

- 1) Subgroups defined by each of the three pre-specified strata (see section 4).
- 2) Subgroups defined by gender.
- 3) Patients who are prescribed continuous positive airway pressure and use <4 hours per night in the 90 days before the outcome period.
- 4) The subgroup of patients who are prescribed continuous positive airway pressure and use ≥ 4 hours per night in the 90 days before the outcome period.

10. Adverse and Serious Adverse Event Monitoring:

To ensure unbiased determination across arms at 12- and 21-month follow-up, we will ask participants to complete a survey about potential adverse events (AE), serious adverse events (SAE) and unanticipated problems (UP) employing a body system-based assessment. We define SAEs as those resulting in hospitalization or death.

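### Two planned subgroups are defined by CPAP use after randomization, so arm comparisons inside them are not protected by randomization

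*SAP*

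**What the plan says.** SAP section 9 (Additional Analytic Subgroups) states that "we will analyze primary and secondary outcomes according to model 1 and model 2 in the following groups". Items 1 and 2 are the stratification factors and gender. Item 3 is "Patients who are prescribed continuous positive airway pressure and use <4 hours per night in the 90 days before the outcome period". Item 4, worded the same way in protocol 5.6.2, is "The subgroup of patients who are prescribed continuous positive airway pressure and use ≥4 hours per night in the 90 days before the outcome period".

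The same variable has other roles in the plan:

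- Protocol Table 5 places objective PAP adherence and self-reported treatment adherence among the secondary effectiveness outcomes. SAP section 3 also names treatment adherence as a secondary outcome.
- Protocol 5.5.3 says: "We will explore the impact of weight loss on PAP usage and will assess PAP use as a mediator in secondary analyses".
- On timing, protocol 5.5.3 says "We will collect 90-day PAP adherence at 3, 12 and 21 months" and "We also collect self-reported adherence to PAP and other treatments at 3, 12, and 21 months". Table 5 also marks both at baseline.
- Protocol 5.3.5 leaves PAP prescribing to usual care in both arms.

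The one model written out in SAP section 9 has no treatment main effect. Its intercept is described as the average baseline value "among the control and treatment groups combined (assumed equal due to randomization").

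**The concern.** A subgroup comparison keeps the protection of randomization when membership is fixed before assignment or cannot be affected by it. Strata and gender meet that condition. CPAP hours during follow-up do not. If the intervention moves some patients across the 4-hour line, or on or off a prescription, the patients found in a subgroup in one arm are a different selection from those found in it in the other arm.

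The written model adds a second difficulty. It forces equal baseline means in the two arms and justifies this by randomization, a justification that does not carry over to groups selected on later behaviour.

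Readers will ask whether the intervention helps patients who do, or do not, use CPAP, and items 3 and 4 are the only listed subgroups on that question. Read as treatment effects, they could show a difference that is not real, or understate one that is.

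**Working it through.** **Timing.** Counting 90 days back from 3, 12 and 21 months gives months 0–3, 9–12 and 18–21. If the outcome period is instead taken to open at month 9, the start of the 12-month weight window, the look-back is months 6–9. Every reading falls after randomization.

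**The plan's own figure.** For FOSQ (difference 0.75, SD 2.5, two-sided alpha 0.025, power 0.90) a two-sample t-test needs 556 evaluable patients, as stated in SAP Table 1; 556/0.80 = 695, against 696 planned. That calculation is sound and is not touched by this point. The documents give no size, power or effect for the CPAP subgroups.

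**Illustration of size.** From the documents: FOSQ change SD 2.5 and the 4-hour cut. Assumed: PAP use is a normal latent variable with SD 1; a share p0 = 0.50 of controls is at or above 4 hours; the intervention share is p1 = 0.55 or 0.60; the correlation ρ between PAP use and FOSQ change is 0.3 or 0.5. Let z_p = Φ⁻¹(1−p) and d = z_p0 − z_p1, which is 0.126 or 0.253.

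(a) Correlation from shared causes only, true effect zero:

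- users: ρ × 2.5 × [φ(z_p1)/p1 − φ(z_p0)/p0]
- non-users: −ρ × 2.5 × [φ(z_p1)/(1−p1) − φ(z_p0)/(1−p0)]

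For p1 = 0.60 and ρ = 0.5: users 1.25 × (0.6439 − 0.7979) = −0.192; non-users −1.25 × (0.9659 − 0.7979) = −0.210.

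(b) Correlation fully causal, with the whole effect acting through PAP: add the true effect ρ × 2.5 × d to each line of (a).

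(c) Half and half: the mean of (a) and (b), with half the true effect.

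| p1 | ρ | (a) users / non-users | (b) users / non-users | true effect in (b) | (c) users / non-users | true effect in (c) |
|---|---|---|---|---|---|---|
| 0.55 | 0.3 | −0.059 / −0.061 | +0.036 / +0.033 | 0.094 | −0.012 / −0.014 | 0.047 |
| 0.55 | 0.5 | −0.098 / −0.102 | +0.059 / +0.055 | 0.157 | −0.019 / −0.024 | 0.079 |
| 0.60 | 0.3 | −0.115 / −0.126 | +0.075 / +0.064 | 0.190 | −0.020 / −0.031 | 0.095 |
| 0.60 | 0.5 | −0.192 / −0.210 | +0.124 / +0.107 | 0.317 | −0.034 / −0.052 | 0.158 |

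In (b) each subgroup shows about 34–39% of the true effect; in (c) the sign is wrong. A fall in PAP use reverses the signs.

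**Error rate under (a).** With an even split by arm, SE = 2.5 × √(4/n): 0.300 at n = 278 and 0.424 at n = 139 per subgroup. The probability that |N(bias/SE, 1)| exceeds 1.96 is 5.4–6.3% (5-point rise) or 6.7–10.8% (10-point rise) at n = 278, and 5.2–5.7% or 5.9–7.9% at n = 139.

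**Baseline balance.** If baseline FOSQ correlates 0.3 with later PAP use, dividing the ρ = 0.3 entries in (a) by 2.5 gives a baseline arm difference inside a subgroup of about 0.02 SD (5 points) or 0.05 SD (10 points).

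**Cross-check by simulation.** With assumed use of mean 4 h and SD 2 h and no true effect, no shift in use gave no bias and an error rate of about 5%. A 0.5 h shift gave false differences of about 0.04–0.22 points for ρ from 0.1 to 0.5, and a 1 h shift about 0.07–0.44. The largest error rate, 28–29%, needed a 1 h fall and ρ = 0.5 with 556 patients over the two subgroups. Grouping by pre-randomization use gave bias within 0.006, which is simulation error.

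**The case against.** The strongest reply is that these are additional analyses alongside the intention-to-treat analysis. They carry no hypothesis, alpha or power claim, and the plan never says they will be read causally. That is true; it limits the severity but does not make the comparisons valid. Items 3 and 4 stand beside baseline subgroups, with the same models and no distinction.

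The harm is also conditional and often small. At a 5-point shift it is at most about 0.10 points, or 14% of the 0.75 target, and the baseline imbalance is slight. This stands.

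The illustration has limits too. Two subgroups of 278 use all 556 expected completers, so everyone would need a CPAP prescription and usable data; the 139 row relaxes this. Allowing for the uneven arm split lowers the 10.8% to about 10.1–10.3%. The planned model adjusts for OSA severity, sleep impairment and other covariates, which could absorb part of the shared causes.

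Finally, baseline groups answer a different question, effect by starting PAP status and not by achieved use, and many participants are newly diagnosed (SAP section 1). Both points are fair. They are why follow-up use should stay in the mediation analysis and why a labelling fallback is offered below. Enrolment after reassessment (protocol 5.4) means that some patients may already use PAP at baseline.

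**Conclusion.** The concern holds. Both subgroups are defined by a variable measured after randomization that the plan itself treats as an outcome and possible mediator. Neither document gives a caveat or a causal method for them. There is no distortion if the intervention leaves PAP use and prescription unchanged, or if PAP use is unrelated to the outcome. Otherwise its size and sign cannot be derived from the documents, and the figures above rest on assumed PAP-use rates, correlations and arm shifts. The conclusion rests on the invalid comparison, not on any one of those numbers. The primary tests, alpha and sample size are unaffected. This should be fixed, and the remedy is mainly wording.

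**What to change.** 1. Reconcile Table 5, which marks objective and self-reported PAP adherence at baseline, with protocol 5.5.3, which names only 3, 12 and 21 months. State what baseline PAP data exist. The protocol's change summary for version 2.8 also lists baseline for self-reported adherence.
2. Redefine items 3 and 4 by PAP status before randomization: at least 4 hours, under 4 hours, not on PAP.
3. For this factor, fit one model to all randomized patients with PAP-status main effects, PAP-status-by-time terms and treatment-by-PAP-status-by-time terms. Report the interaction with its confidence interval.
4. Keep follow-up PAP use for the planned mediation analysis.
5. If baseline data are too sparse, or the follow-up groups are kept as well, define the 90-day window and label those results exploratory and not treatment effects.

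The strata and gender subgroups need no change for this reason.

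**Cost.** Wording in both documents, and six more parameters in the two-time-point model (2 main effects, 2 by time, 2 by treatment and time). No new data are needed if the baseline items in Table 5 were collected. Protocol 5.5.3 says "All PAP machines dispensed by VA transmit adherence, with results accessible in routine care through secure platforms", so earlier use may be retrievable for patients already on PAP. The downside is precision: at an assumed 139 patients per level, the difference between two levels' FOSQ effects has SE 0.424 × √2 = 0.60 and a 95% half-width of 1.96 × 0.60 = 1.18 points, wider than the 0.75-point target.

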6.0 Reporting

6.1 Quality monitoring

The investigators will closely monitor and prepare annual summary reports on:

- Patient accrual and follow-up completion/retention in relation to goals and timeline.
- Randomization process and group comparability on the balancing variables.
- Key baseline characteristics of the sample, by blinded group, on the primary and secondary outcome variables.
- Intervention adherence.
- Protocol violations.

6.2 Data Safety and Monitoring Board.

This study will be reviewed regularly (at least annually) by a DSMB convened by the national director of VA HSR&D. This board will monitor the quality of data, progress of recruitment, as well as the incidence of adverse events between arms.

6.3.1. Adverse event monitoring.

To ensure unbiased determination across treatment arms, at 12- and 21-month follow-up contact we will ask participants to complete a survey about potential adverse events (AE), serious adverse events (SAE) and unanticipated problems (UP) employing a body system-based assessment. We define SAEs as those requiring hospitalization or death.

Study staff will collect adverse events using participant self-reports collected at 12 and 21 months. Study staff will also perform chart reviews looking for discharge summaries for the 12 month time period. Study staff will later complete additional chart reviews looking for discharge

summaries for the 21 month time period among patients who do not complete 21 month surveys. [name] or another clinician will assess each AE for duration (start and stop dates and times), expectedness in the study population, severity, outcome, treatment, and relation to study activity.

To account for potential differential survey response rates by arm, we will also query the electronic medical record and compile hospital admissions from randomization through 24 months post randomization. We will report the number of hospitalizations by arm to in our final DSMB report.

The following are expected adverse events in the POWER population of participants who have obstructive sleep apnea, a high BMI, and adopt healthy eating and physical activity program:

- Gastrointestinal symptoms related to change in diet.
- Musculoskeletal symptoms or injury resulting from increased physical activity, including increasing symptoms such as chest discomfort, shortness of breath, and leg cramping.

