- Development of weight and OSA associated medical disorders including diabetes, hypertension, liver disease, cardiovascular disease, cerebrovascular disease, arrhythmias, asthma, COPD, clotting problems, and other lung related conditions;
- Development or exacerbation of mental health conditions, the worsening of which is known to be associated with poor sleep, including depression, anxiety, posttraumatic stress disorder, and bipolar disorder.
- Development or exacerbation of eating disorders including binge eating disorder, anorexia nervosa, and bulimia nervosa.
- Development of other conditions associated with unhealthy health behaviors, such as from tobacco and alcohol disorders (e.g., cancer).
- Age related illnesses, such as pneumonia, urinary tract, and skin infections.
- Motor vehicle collision or other accidents arising from excessive sleepiness.
- Death

Upon discovering an unexpected and related SAE, study staff will provide the IRB and DSMB with a report describing the duration (start and stop dates and times), severity, outcome, treatment, and relation to study activity, according to the required timelines. The DSMB may request additional information if it deems additional deliberation is warranted.

For all other events, staff will summarize and report to the DSMB on an annual basis the numbers and types of all AEs by unidentified treatment arms. At their discretion, the DSMB may request unblinded results to determine the nature and extent of effect of the intervention. Should the DSMB make this request, we will maintain blinding of the investigators and the staff involved in follow-up data collection and analysis. If, at any time, the investigators believe they are seeing an unexpected increase in SAEs that is a cause of concern, they will bring this to the attention of the DSMB.

For annual reporting, staff also will provide the quality monitoring report to the DSMB.

At the annual meeting, the DSMB will review AE/SAEs and the quality of data, as well as review study progress and provide objective recommendations, as appropriate, with respect to:

- Determination of any actions to be taken in response to SAEs.
- Reports related to study operations and the quality of the data.
- Consideration of early termination of the study because of treatment safety concerns or inadequate performance.

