[name] or another licensed independent provider with experience reviewing AEs in clinical trials, [name] ARNP, will assess (using participant self-report and chart review) each AE for duration (start and stop dates and times), expectedness in the study population, severity, outcome, treatment, and relation to study activity for each patient. We will also perform chart reviews at 12 and 21 months to look for discharge summaries within the VA.

The following are expected adverse events in the POWER population of participants who have OSA, a high BMI, and adopt healthy eating and physical activity program:

- Gastrointestinal symptoms related to change in diet
- Musculoskeletal symptoms or injury resulting from increased physical activity, including increasing symptoms such as chest discomfort, shortness of breath, and leg cramping

- Development of weight and OSA associated medical disorders including diabetes, hypertension, liver disease, cardiovascular disease, cerebrovascular disease, arrhythmias, asthma, COPD, clotting problems, and other lung related conditions
- Development or exacerbation of mental health conditions, the worsening of which is known to be associated with poor sleep, including depression, anxiety, posttraumatic stress disorder, and bipolar disorder
- Development or exacerbation of eating disorders including binge eating disorder, anorexia nervosa, and bulimia nervosa.
- Development of other conditions associated with unhealthy health behaviors, such as from tobacco and alcohol disorders (e.g., cancer)
- Age related illnesses, such as pneumonia, urinary tract, and skin infections
- Motor vehicle collision or other accidents arising from excessive sleepiness
- Death

Summary of Edits:

Version 2.0, 11/23/2021

- Minor format changes and typo corrections
- **Section 3. Description of how data will be collected:**
 - Added use of email for recruitment and online questionnaire collection (Qualtrics)
- **Section 4. Method of Randomization:**
 - Removed rural vs. urban strata
 - Redefined physiologic OSA severity strata
 - Added sleep related impairment strata
- Section 10.
 - Added [name] ARNP as additional reviewer of AEs

Version 3.0 2/16/2023

- Minor format changes and clarification that this is a “lifestyle intervention”
- Section 2. Sample Size Rationale

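### Serious adverse events are defined only by hospitalization or death, so an unexpected, study-related, life-threatening or disabling event treated without admission gets no individual report to the IRB and DSMB

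*SAP*

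**What the plan says.** SAP section 10 states: "We define SAEs as those resulting in hospitalization or death". Protocol 6.3.1 states: "We define SAEs as those requiring hospitalization or death". The verb differs, but the two criteria are the same. Neither document adds a life-threatening, disability or medical-judgement criterion.

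The reporting rules are in protocol 6.3.1 only; the SAP has none.

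- **Individual report:** "Upon discovering an unexpected and related SAE, study staff will provide the IRB and DSMB with a report describing the duration", along with severity, outcome, treatment and relation to the study.
- **Everything else:** "For all other events, staff will summarize and report to the DSMB on an annual basis the numbers and types of all AEs", presented by unidentified arm.
- **Escalation at the investigators' initiative:** "If, at any time, the investigators believe they are seeing an unexpected increase in SAEs that is a cause of concern", they take it to the DSMB.

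Protocol 6.2 has the DSMB meet at least once a year. Under 6.3.1 it reviews AEs and SAEs at the annual meeting and decides on any action in response to SAEs.

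Both documents say a clinician assesses each AE for duration, expectedness, severity, outcome, treatment and relation to the study. Both also carry a list of expected events. It covers gastrointestinal symptoms, exercise-related injury, cardiovascular disease and arrhythmias, mental-health conditions, eating disorders, accidents due to sleepiness, and death.

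**The concern.** The route to a prompt report starts with the SAE label, and that label depends on where the event was treated, or on death, rather than on how dangerous or lasting it was. A participant may have a life-threatening episode, or be left with a lasting disability, after emergency or outpatient care alone. As written, that event is not serious. However surprising it is, and however clearly it is tied to the programme, no individual report is required.

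What is at stake is how soon the DSMB learns of a new harm and how that harm is labelled when it does. The intervention is remote and self-directed, a subset of participants pauses treatment for one night for the home sleep test, and no interim analysis is planned. DSMB safety review is therefore the main trial-level safeguard. A new harm that happens not to involve admission would reach the board as one line in an annual count of AE types.

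**Working it through.** No sample size, error rate or event count enters this point. The check is to take each kind of event through protocol 6.3.1, first with the current definition and then with a definition that also covers life-threatening, disabling or medically important events.

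The rule has three conditions, and all must hold for an individual report: the event is an SAE, it is unexpected, and it is related.

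| Event | Route now | Route under the wider definition |
|---|---|---|
| Admitted or fatal; unexpected and related | Individual report | Unchanged |
| Admitted or fatal; expected or unrelated | Annual summary | Unchanged |
| Not admitted, but life-threatening, disabling or medically important; unexpected and related | Annual summary, as an AE | Individual report |
| Same seriousness, not admitted; expected or unrelated | Annual summary, as an AE | Annual summary, as an SAE |
| Not admitted, none of these features | Annual summary | Unchanged |

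The timing of the report changes only in the third row. In the fourth row only the classification changes.

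**Which harms fall in which row.** Eating disorders, mental-health conditions, arrhythmias, injury from increased activity, and collisions ("Motor vehicle collision or other accidents arising from excessive sleepiness") are all on the expected list. They belong in the fourth row unless the reviewing clinician judges a particular case unexpected despite the list. The third row holds harms that are not listed. One illustration, which is an assumption and not an event described in the documents: protocol 5.3.6.1 advises a daily calorie reduction, Table 4 does not list diabetes among the exclusions, and hypoglycaemia is not on the expected list. A dangerous episode judged related to the programme, treated in an emergency department and sent home, would sit in the third row.

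**Whether another stated route catches the third row.**

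- The escalation clause is worded in terms of SAEs, so it uses the same definition.
- Unanticipated problems are asked about in the survey, but neither document gives them a reporting rule of their own.
- Severity is assessed for every AE, but no reporting step depends on it.
- The 24-month record query compiles hospital admissions, so by design it does not see these events.
- Protocol 5.5.4 (eating-disorder symptoms), 5.5.5 (concerning sleep-test findings) and 5.7 (ceasing intervention activities) lead to contact with the participant or provider, or to ending intervention activities. None of them sends the event to the DSMB.

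**Size of the delay.** With one summary every 12 months, an event discovered just after a summary waits up to about 12 months, and one discovered just before waits almost none. If discoveries were spread evenly over the year (an assumption), the mean wait would be 12 / 2 = 6 months. The wait is shorter if the board meets more often than once a year. It starts at discovery: general AE self-report takes place only at 12 and 21 months, so time may already have passed.

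**The case against.** The strongest counter-argument is that the gap is narrow and the definition has a rationale.

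*The expected list.* A reader might infer that serious outpatient harms in general lose a prompt report: an eating disorder, a psychiatric crisis, an arrhythmia, a collision, an exercise injury. The documents do not support that. All of these are listed as expected, and expected events go to the annual summary even when they are SAEs. This part of the objection stands and limits the point to unexpected, related events.

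*The arm comparison.* A reader might also infer that a by-arm comparison of serious events exists and omits these cases. No such table is specified. The plan promises annual numbers and types of all AEs by unidentified arm, and a by-arm count of hospitalizations in the final DSMB report. A non-admitted event is still counted in the first. This stands too.

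*Ascertainment.* Admission and death can be checked in records. Non-admitted events rest mainly on self-report at 12 and 21 months, because chart review looks for discharge summaries. Protocol 6.3.1 is itself concerned that survey response may differ by arm, and participants know their assignment. Restricting SAEs to verifiable outcomes is therefore a defensible choice for comparing arms. It is not a reason to withhold an individual report once an event is known. This part shapes the fix but does not remove the gap.

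*Unseen rules.* The protocol's summary of edits mentions a DSMB charter and a DSMB analysis plan, neither of which is among the documents, and IRB rules may cover unanticipated problems. Some events may be caught there. The protocol and SAP do not say so.

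*Participant safeguards.* The steps in protocol 5.5.4, 5.5.5 and 5.7 do protect the individual. They do not inform the board.

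**Conclusion.** The point holds in a limited form. On the current wording of both documents, an event that is unexpected, study-related, and life-threatening or disabling, but treated without admission, has no stated prompt route to the IRB and DSMB. It is not an SAE in the DSMB's annual review or under the escalation clause. For expected or unrelated events of the same seriousness, only the label is affected.

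The consequence is a delay of up to about 12 months after discovery, assuming yearly summaries. The number of participants affected is not given and is probably small. Nothing here shows that an arm comparison is biased or that a planned serious-event analysis loses data.

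The conclusion rests on the protocol and SAP alone and would weaken if the DSMB charter sets a wider definition or a separate rule for unanticipated problems. It does not rest on any outside regulatory standard. The change is worth making because the existing rule gives a worse safety result than intended for the one class of event it misses, and correcting it is cheap.

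**What to change.** In SAP section 10 and protocol 6.3.1, use one common wording for the SAE definition. Extend it beyond death and hospitalization to events that are life-threatening, that cause persistent or significant disability, or that the reviewing clinician judges medically important. Apply the existing individual-report rule, the escalation clause and the DSMB's annual SAE review to that definition.

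Keep hospitalizations and deaths as a separately reported by-arm count, so that the record-verifiable component is not mixed with events that may be ascertained differently by arm.

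If the DSMB charter already covers these events, cite it in both documents and align the definitions.

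The cost is wording in two places, one extra seriousness judgement per AE made from assessments the clinician already records, and a few more individual reports. Events already recorded can be reclassified before the final DSMB report. The downside is an added SAE component with weaker ascertainment. The change improves classification and reporting once an event is known; it does not improve detection of events treated without admission.
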